| Statistical Methods: | 
Non inferiority testing will only be carried out with seropositive subjects and providing that the number of evaluable subjects attains a global power of at least 80%. This applies to the co-primary objectives, and the secondary objective. Otherwise, descriptive analyses will be performed.
 
Primary Objectives:
 
Tdap immunogenicity
 
A non-inferiority testing approach will be used to compare geometric mean concentrations (GMCs) for PT, FHA, PRN, FIM2+3, 28 days after the booster dose of Tdap, for each antigen “i” based on the following individual hypotheses:
 $H_0^i: \text{GMC}_{\text{Group1}}^i / \text{GMC}_{\text{Group2}}^i \leq \frac{1}{\delta} \Leftrightarrow \log_{10}(\text{GMC}_{\text{Group1}}^i) - \log_{10}(\text{GMC}_{\text{Group2}}^i) \leq -\log_{10}(\delta)$ $H_1^i: \text{GMC}_{\text{Group1}}^i / \text{GMC}_{\text{Group2}}^i > \frac{1}{\delta} \Leftrightarrow \log_{10}(\text{GMC}_{\text{Group1}}^i) - \log_{10}(\text{GMC}_{\text{Group2}}^i) > -\log_{10}(\delta)$ 
with:
 
i, antigen {PT, FHA, PRN, FIM 2+3}.
 
<math>\delta</math>, non-inferiority limit is set at 1.5, i.e., 0.176 (<math>=\log_{10} [1.5]</math>), for each antigen “i”.
 
Non-inferiority for antigen “i” will be demonstrated if the lower bound of the 2-sided 95% CI is greater than <math>-\delta</math>. For each of the 4 antigens, the statistical methodology will be based on the use of the age-stratified two-sided 95% CI of the ratio of GMCs between groups. The age-stratified CI will be calculated using an ANOVA model (type II analysis) of <math>\log_{10}</math>-transformed titers. The age groups (9 to 11 years, 12 to 17 years, 18 to 45 years and 46 to 60 years) will be used as the stratifying factor in the model.
 
Additionally, a non-inferiority testing approach will be used to compare seroprotection rates of T and D, 28 days after the booster dose of Adacel®. Seroprotection is defined as anti-D and anti-T Ab concentration superior to 0.1 IU/mL.
 
The individual tested hypotheses for the antigen “i” will be as follows:
 $H_0^i: P_{\text{Group1}}^i - P_{\text{Group2}}^i \leq -\delta$ $H_1^i: P_{\text{Group1}}^i - P_{\text{Group2}}^i > -\delta$ 
Where the non-inferiority limit <math>\delta</math> is set at 10% for both T and D concentrations <math>\geq 0.1</math> IU/mL.
 
Non-inferiority for antigen “i” will be demonstrated if the lower bound of the 2-sided 95% CI is greater than <math>-\delta</math>.
 
The non-inferiority test will be performed using the 95% 2-sided CI of the difference between Group 1 and Group 2 for seroprotection rates and of the differences of the means of the <math>\log_{10}</math> transformed post-vaccination concentrations/titers for GMCs (<math>\alpha=2.5\%</math> one-sided). The 95% CI will be calculated based on the Wilson score method without continuity correction as quoted by Newcombe for seroprotection rates and using the normal approximation of the <math>\log_{10}</math> transformed post-vaccination titers for GMCs.
 
CYD dengue vaccine immunogenicity
 
A non-inferiority testing approach will be used to compare geometric mean titers (GMTs), for dengue serotypes 1, 2, 3, and 4, 28 days after the first injection of CYD dengue vaccine between Group 1 and Group 2 for each serotype “i” based on the following individual hypotheses:
 $H_0^i: \text{GMT}_{\text{Group1}}^i / \text{GMT}_{\text{Group2}}^i \leq \frac{1}{\delta} \Leftrightarrow \log_{10}(\text{GMT}_{\text{Group1}}^i) - \log_{10}(\text{GMT}_{\text{Group2}}^i) \leq -\log_{10}(\delta)$ $H_1^i: \frac{1}{\delta} < \text{GMT}_{\text{Group1}}^i / \text{GMT}_{\text{Group2}}^i > \frac{1}{\delta} \Leftrightarrow \log_{10}(\text{GMT}_{\text{Group1}}^i) - \log_{10}(\text{GMT}_{\text{Group2}}^i) > -\log_{10}(\delta)$ |

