###### Individual hypotheses on Tdap response for each antigen:

A non-inferiority testing approach will be used to compare geometric mean concentrations (GMCs) for PT, FHA, PRN, FIM2+3, 28 days after the booster dose of Tdap, for each antigen “i” based on the following individual hypotheses:

$$H_0^i: \text{GMC}_{\text{Group1}}^i / \text{GMC}_{\text{Group2}}^i \leq \frac{1}{\delta} \Leftrightarrow \log_{10}(\text{GMC}_{\text{Group1}}^i) - \log_{10}(\text{GMC}_{\text{Group2}}^i) \leq -\log_{10}(\delta)$$

$$H_1^i: \text{GMC}_{\text{Group1}}^i / \text{GMC}_{\text{Group2}}^i > \frac{1}{\delta} \Leftrightarrow \log_{10}(\text{GMC}_{\text{Group1}}^i) - \log_{10}(\text{GMC}_{\text{Group2}}^i) > -\log_{10}(\delta)$$

with:

i, antigen {PT, FHA, PRN, FIM 2+3}.

$\delta$ , non-inferiority limit is set at 1.5, i.e., 0.176 ( $=\log_{10} [1.5]$ ), for each antigen “i”.

Non-inferiority for antigen “i” will be demonstrated if the lower bound of the 2-sided 95% confidence interval (CI) is greater than  $\delta$  ( $\alpha=2.5\%$  one-sided). For each of the 4 antigens, the statistical methodology will be based on the use of the age-stratified two-sided 95% CI of the ratio of GMCs between groups. The age-stratified CI will be calculated using an ANOVA model (type II analysis) of  $\log_{10}$ -transformed titers. The age groups (9 to 11 years, 12 to 17 years, 18 to 45 years and 46 to 60 years) will be used as the stratifying factor in the model.

Additionally, a non-inferiority testing approach will be used to compare seroprotection rates of T and D, 28 days after the booster dose of Tdap vaccine. Seroprotection is defined as anti-D and anti-T Ab concentration superior to 0.1 IU/mL.

The individual tested hypotheses for the antigen “i” will be as follows:

$$H_0^i: P_{Group1}^i - P_{Group2}^i \leq -\delta$$

$$H_1^i: P_{Group1}^i - P_{Group2}^i > -\delta$$

with:

i, antigen {T, D}

$\delta$ , non-inferiority limit is set at 10% for both T and D.

Non-inferiority for antigen “i” will be demonstrated if the lower bound of the 2-sided 95% CI is greater than  $-\delta$ .

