5.1.1 Hypotheses and Statistical Methods for Primary Objectives

5.1.1.1 Hypotheses

Non-inferiority on Tdap vaccine

The objective is to demonstrate that the humoral immune response to the Tdap booster dose administered concomitantly with the first dose of CYD dengue vaccine is non-inferior to the humoral immune response to the Tdap booster dose administered alone 28 days before the first dose of CYD dengue vaccine.

Individual hypotheses on Tdap response for each antigen:

A non-inferiority testing approach will be used to compare geometric mean concentrations (GMCs) for PT, FHA, PRN, FIM2+3, 28 days after the booster dose of Tdap, for each antigen “i” based on the following individual hypotheses:

$$H_0^i: GMC_{Group1}^i / GMC_{Group2}^i \leq \frac{1}{\delta} \Leftrightarrow \log_{10}(GMC_{Group1}^i) - \log_{10}(GMC_{Group2}^i) \leq -\log_{10}(\delta)$$

$$H_1^i: GMC_{Group1}^i / GMC_{Group2}^i > \frac{1}{\delta} \Leftrightarrow \log_{10}(GMC_{Group1}^i) - \log_{10}(GMC_{Group2}^i) > -\log_{10}(\delta)$$

with:

i, antigen {PT, FHA, PRN, FIM 2+3}.

δ , non-inferiority limit is set at 1.5, i.e., 0.176 ($=\log_{10} [1.5]$), for each antigen “i”.

Non-inferiority for antigen “i” will be demonstrated if the lower bound of the 2-sided 95% confidence interval (CI) is greater than δ ($\alpha=2.5\%$ one-sided). For each of the 4 antigens, the statistical methodology will be based on the use of the age-stratified two-sided 95% CI of the ratio of GMCs between groups. The age-stratified CI will be calculated using an analysis of variance (ANOVA) model (type II analysis) of \log_{10} -transformed titers. The age groups (9 to 11 years, 12 to 17 years, 18 to 45 years and 46 to 60 years) will be used as the stratifying factor in the model.

Additionally, a non-inferiority testing approach will be used to compare seroprotection rates of T and D, 28 days after the booster dose of Tdap vaccine. Seroprotection is defined as anti-D and anti-T Ab concentration superior to 0.1 IU/mL.

The individual tested hypotheses for the antigen “i” will be as follows:

$$H_0^i: P_{Group1}^i - P_{Group2}^i \leq -\delta$$

$$H_1^i: P_{Group1}^i - P_{Group2}^i > -\delta$$

with:

i, antigen {T, D}

δ , non-inferiority limit is set at 10% for both T and D.

Non-inferiority for antigen “i” will be demonstrated if the lower bound of the 2-sided 95% CI is greater than $-\delta$.

Global hypotheses for non-inferiority on Tdap response:

The global hypotheses are:

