H_{0G} : Non inferiority of Tdap booster dose co-administered with the first dose of CYD dengue vaccine versus Tdap booster dose administered alone is not demonstrated for at least one antigen.

H_{1G} : Non-inferiority of Tdap booster dose co-administered with the first dose of CYD dengue vaccine versus Tdap booster dose administered alone is demonstrated for all the antigens.

H_0^G : at least one H_0^i not rejected

H_1^G : all H_0^i are rejected

Non-inferiority on CYD dengue vaccine after 1 dose

The objective is to demonstrate that the humoral immune response to the first dose of CYD dengue vaccine administered concomitantly with Tdap booster dose is non-inferior to the humoral immune response to the first dose of CYD dengue vaccine administered sequentially 28 days after the Tdap booster dose.

Individual hypotheses on CYD response after one dose for each serotype:

A non-inferiority testing approach will be used to compare geometric mean of titers (GMTs), for dengue serotypes 1, 2, 3, and 4, 28 days after the first injection of CYD dengue vaccine between Group 1 and Group 2 for each serotype “i” based on the following individual hypotheses:

$$H_0^i: \text{GMT}_{Group1}^i / \text{GMT}_{Group2}^i \leq \frac{1}{\delta} \Leftrightarrow \log_{10}(\text{GMT}_{Group1}^i) - \log_{10}(\text{GMT}_{Group2}^i) \leq -\log_{10}(\delta)$$

$$H_1^i: \text{GMT}_{Group1}^i / \text{GMT}_{Group2}^i > \frac{1}{\delta} \Leftrightarrow \log_{10}(\text{GMT}_{Group1}^i) - \log_{10}(\text{GMT}_{Group2}^i) > -\log_{10}(\delta)$$

with:

i, serotypes in {1, 2, 3, 4}.

δ , non-inferiority limit is set at 2, i.e., 0.301 ($=\log_{10} [2]$), for each serotype “i”.

Non-inferiority for serotype “i” will be demonstrated if the lower bound of the 2-sided 95% CI is greater than $-\delta$.

Global hypotheses for non-inferiority on CYD response after one dose:

H_0^G : at least one H_0^i not rejected

H_1^G : all H_0^i are rejected

Overall, non-inferiority among the groups will be demonstrated if, for each antigen of Tdap and each serotype of CYD dengue vaccine, the two-sided 95% CI lies above $-\delta$.

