5.5 Determination of Sample Size and Power Calculation

Power calculation is based on initial sample size of the trial. 688 subjects were to be enrolled regardless of dengue baseline status: 344 subjects per treatment group (86 subjects per age group).

Considering a potential attrition rate of 10%, such sample size would provide 618 evaluable subjects in the PPAS of Tdap and CYD dengue vaccine (PPT and PPC). This will give, for the co-primary objectives, a global power over 90.0% for the testing of non-inferiority (based on SAS proc Power).

The following assumptions were considered for the non-inferiority on Tdap: an alpha level of 2.5% (one-sided hypotheses), a maximum acceptable difference of 0.176 for GMCs, and of 10% for seroprotection rates, and assuming the following rates and standard deviations (SDs):

- $T \geq 0.1$ IU/mL – 99% of subjects
- $D \geq 0.1$ IU/mL – 99% of subjects
- PT SD – 0.4
- FHA SD – 0.4
- PRN SD – 0.5
- FIM2+3 SD – 0.6

(based on TD519, TD506 and TD526 studies and on Keith S. Reisinger (4)).

The following assumptions were considered for the non-inferiority after the first dose of CYD dengue vaccine: an alpha level of 2.5% (one-sided hypotheses), a maximum acceptable difference of 0.301 for GMTs, and assuming a standard deviation of 1.0 for serotype 1, 0.8 for serotypes 2 and 3, 0.7 for serotype 4 (based on CYD22 and CYD47 studies conducted in Asia Pacific).

In addition, this sample size would have given for the non-inferiority after the third dose* of CYD dengue vaccine (on PPC3), considered as a secondary objective, a global power over 99.0% for the testing of non-inferiority (based on SAS proc Power).

The following assumptions were considered for the non-inferiority after the third dose* of CYD dengue vaccine: an alpha level of 2.5% (one-sided hypotheses), a maximum acceptable difference of 0.301 for GMTs, and assuming a standard deviation of 0.8 for serotypes 1 and 2, 0.7 for serotypes 3 and 4 (based on studies conducted in Asia Pacific).

* Analysis on the 3rd dose will not be done due to the early termination of study (cf. section 5.7)

Table 5.2: Powers for Non-inferiority between GMT/seroprotection for each antigen and serotype - Primary objective

Antigen/Serotype	Alpha	δ	Reference rate/SD	Power (%) for 309 evaluable subjects per group
D	0.025	10%	99%	> 99.9
T	0.025	10%	99%	> 99.9
PT	0.025	0.176	0.4	> 99.9
FHA	0.025	0.176	0.4	> 99.9
PRN	0.025	0.176	0.5	99.2
FIM2+3	0.025	0.176	0.6	95.4

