- The first interim analysis scheduled on results obtained after a partial database lock of data collected up to the 28 days post first dose of CYD dengue vaccine at V03, M2) was not done due to the hold of the study.
 - The potentially second interim analyses scheduled on results collected up to the 28 days after the third dose CYD dengue vaccine at V06, M13 was not performed because no subjects received the third CYD dose.
 - Only one final statistical analysis will be performed.
- 5.5 Determination of the sample size and power calculation:

Considering a potential attrition rate of 10%, it was initially planned that such sample size would provide 618 evaluable subjects in the PPAS of Tdap and CYD dengue vaccine (PPT and PPC). This sample size (based on SAS proc Power) targeted a global power over 90.0% for the non-inferiority testing corresponding to the co-primary objectives (i.e., after the booster dose of Tdap and after the first dose of CYD), and over 99.0% for the non-inferiority corresponding to the secondary objective (ie, testing after the third dose of CYD dengue vaccine).

However, with early termination of the study, since the number of evaluable subjects will be reduced (ie, number of dengue seropositive subjects in PPT and PPC), reducing global power to 80% may be considered. Thus, the non-inferiority testing will be carried out only if a global power of at least 80% for the co-primary objectives can be attained (i.e., if the number of evaluable subjects is at least 510 for the co-primary objectives and 324 for the secondary objective). (table 5.4 and 5.5)

Table 5.4: Powers for Non-inferiority between GMT/seroprotection for each antigen and serotype - Primary objective

Antigen/Serotype	Alpha	δ	Reference rate/SD	Power (%) for 309 evaluable subjects per group	Power (%) for 255 evaluable subjects per group
D	0.025	10%	99%	> 99.9	> 99.9
T	0.025	10%	99%	> 99.9	> 99.9
PT	0.025	0.176	0.4	> 99.9	> 99.9
FHA	0.025	0.176	0.4	> 99.9	> 99.9
PRN	0.025	0.176	0.5	99.2	97.8
FIM2+3	0.025	0.176	0.6	95.4	91.1
Dengue serotype 1	0.025	0.301	1.0	96.2	92.4
Dengue serotype 2	0.025	0.301	0.8	99.7	98.9
Dengue serotype 3	0.025	0.301	0.8	99.7	98.9
Dengue serotype 4	0.025	0.301	0.7	> 99.9	99.8
Global power				90%	80%

Table 5.5: Powers for Non-inferiority between GMT for each serotype - Secondary objective

Serotype	Alpha	δ	Reference SD	Power (%) for 309 evaluable subjects per group	Power (%) for 162 evaluable subjects per group

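### The SAP's pertussis success sentence omits the minus sign before δ, so the written threshold contradicts the hypotheses it is meant to test

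*SAP*

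**What the plan says.** SAP 5.1.1.1 (Non-inferiority on Tdap vaccine) tests each pertussis antigen against a GMC ratio, Group 1 over Group 2, of 1/δ. It also writes this as a log10 difference of −log10(δ). The margin δ is given as 1.5, or 0.176 on the log10 scale. The success sentence that follows declares non-inferiority if the "lower bound of the 2-sided 95% confidence interval (CI) is greater than δ".

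Elsewhere in the same section the sign is present:

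- The success sentence for tetanus and diphtheria uses −δ.
- The success sentence for the dengue serotypes uses −δ.
- The overall rule requires that, "for each antigen of Tdap and each serotype of CYD dengue vaccine, the two-sided 95% CI lies above" −δ.

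The protocol is split. Section 12.1.1.1 has the pertussis sentence, "if the lower bound of the 2-sided 95% confidence interval (CI) is greater than", followed by an unsigned δ. The synopsis (Statistical Methods) gives the pertussis rule with −δ.

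SAP 5.5 states the margin without a sign, as "a maximum acceptable difference of 0.176 for GMCs, and of 10% for seroprotection rates". The power tables likewise list 0.176.

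**The concern.** The hypotheses and the success sentence cannot both be the rule. A lower bound above −0.176 is a non-inferiority criterion. A lower bound above +0.176 requires Group 1 to be shown superior by more than a factor of 1.5.

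The sentence sets the antigen-level threshold for PT, FHA, PRN and FIM2+3. These are four of the ten co-primary comparisons: four pertussis antigens, T, D and four dengue serotypes. Every one must succeed, so an analysis that followed the sentence would make the Tdap objective and the overall claim practically unattainable when the groups respond equally. If the sign is instead put right silently in programming, the applied criterion differs from the written one. SAP 5.7 plans a single final analysis, so no earlier analysis would bring the discrepancy to light.

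**Working it through.** **1. The statements side by side**

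| Place | Boundary for the lower limit |
|---|---|
| SAP 5.1.1.1, H0/H1 for pertussis | −log10(δ) = −log10(1.5) = −0.176 |
| SAP 5.1.1.1, pertussis success sentence | +δ |
| SAP 5.1.1.1, T and D success sentence | −δ |
| SAP 5.1.1.1, dengue success sentence | −δ |
| SAP 5.1.1.1, overall rule, each Tdap antigen included | −δ |
| Protocol 12.1.1.1, pertussis success sentence | +δ |
| Protocol synopsis, pertussis rule | −δ |

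A text-extraction fault is unlikely. Neighbouring expressions in the same section keep the sign, and the protocol body, a separate document, lacks it in the same sentence.

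**2. Inputs for the power check**

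The inputs come from SAP 5.5 and Table 5.4 in SAP 5.7:

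- One-sided alpha is 0.025.
- The pertussis margin is 0.176, with SD 0.4 for PT and FHA, 0.5 for PRN and 0.6 for FIM2+3.
- The dengue margin is 0.301, with SD 1.0 for serotype 1, 0.8 for serotypes 2 and 3, and 0.7 for serotype 4.
- There are 255 or 309 evaluable subjects per group.

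Assumptions: true log10 difference 0; an unstratified two-sample t comparison; T and D powers taken as 1, since the tables print > 99.9.

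**3. Reproducing the plan's figures with the boundary at −0.176 (dengue −0.301)**

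se = SD × √(2/n), df = 2n − 2. Power is the upper tail of the noncentral t beyond t(0.975, df), with noncentrality margin/se.

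Example, FIM2+3 at 255 per group: se = 0.6 × √(2/255) = 0.0531; noncentrality = 0.176/0.0531 = 3.31; power 91.1%.

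| Comparison | 255: computed | 255: printed | 309: computed | 309: printed |
|---|---|---|---|---|
| PT, FHA | 99.86% | > 99.9 | 99.98% | > 99.9 |
| PRN | 97.8% | 97.8 | 99.2% | 99.2 |
| FIM2+3 | 91.1% | 91.1 | 95.4% | 95.4 |
| Dengue 1 | 92.4% | 92.4 | 96.2% | 96.2 |
| Dengue 2, 3 | 98.9% | 98.9 | 99.7% | 99.7 |
| Dengue 4 | 99.8% | 99.8 | 99.96% | > 99.9 |
| Product (global) | 80.1% | 80% | 90.3% | 90% |

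The only gap is PT and FHA at 255 per group, where 99.86% is printed as > 99.9. It does not affect the point.

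**4. The sentence as written, boundary +0.176**

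The calculation is the same with noncentrality −0.176/se.

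| Antigen | P(success), 255 per group | P(success), 309 per group |
|---|---|---|
| FIM2+3 | 7.0e-8 | 1.1e-8 |
| PRN | 1.5e-9 | 1.2e-10 |
| PT, FHA (each) | 2.3e-12 | 5.8e-14 |

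**5. Observed GMC ratio needed at 255 per group**

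Ratio = 10^(boundary + t × se), with t(0.975, 508) = 1.965.

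| Antigen | se | As written (+0.176) | Intended (−0.176) |
|---|---|---|---|
| FIM2+3 | 0.0531 | 1.91 | 0.85 |
| PRN | 0.0443 | 1.83 | 0.81 |
| PT, FHA | 0.0354 | 1.76 | 0.78 |

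The printed powers therefore belong to a boundary of −0.176. The unsigned 0.176 in SAP 5.5 and the tables does not contradict the sentence on its face, but the powers built on it do.

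**The case against.** The strongest reply is that this is a typographical slip which the SAP already resolves. H0 and H1 fix the boundary at −log10(δ). The global Tdap hypothesis is defined through rejection of those H0s, the overall rule repeats −δ for each Tdap antigen, and the objective is called non-inferiority throughout. An analyst would have to set all of that aside to apply +δ. The tiny probabilities describe a test nobody intends, and they come from an unstratified comparison, whereas the SAP specifies an ANOVA stratified by age group.

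Most of this is fair. The intent is recoverable, the error is conservative, and the probabilities and ratios apply only to a literal reading. The unstratified calculation makes the required ratios approximate, although it reproduces the plan's own powers. What the reply does not remove is the contradiction: the sentence whose job is to state the success threshold states the wrong one, and in a confirmatory analysis that threshold should not have to be inferred from other sentences.

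**Conclusion.** The point holds. The pertussis success sentence in SAP 5.1.1.1 gives the wrong boundary for four of the ten co-primary comparisons. Read literally, it turns pertussis power of 91.1% or more at 255 per group into at most 7.0e-8 per antigen under equal responses.

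The error cannot inflate false claims, because any lower bound above +0.176 is also above −0.176. It should be fixed, but it is a wording error and not a flaw in the design or sample size.

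The finding rests on the contradiction inside the SAP. The SAP says it is based on protocol version 1.0, which is not among the documents supplied. The protocol text cited here is that of Amendment 1 and serves only as corroboration. The power figures assume the plan's SDs, a zero true difference and a two-sample t comparison.

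**What to change.** In SAP 5.1.1.1, replace the pertussis success sentence with wording such as: non-inferiority for antigen i is shown if the lower bound of the two-sided 95% CI of the log10 GMC difference (Group 1 minus Group 2) is greater than −0.176, equivalently if the lower bound for the GMC ratio is greater than 1/1.5 = 0.667.

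Naming the scale matters as well as the sign. The section gives δ as both 1.5 and 0.176 and speaks of a CI for the ratio; on the ratio scale, a limit of −1.5 would be met by any result.

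Correct the same sentence in Protocol 12.1.1.1 alongside it. As an optional clarification, write the limits in the overall rule as numbers: −0.176 for pertussis, −0.301 for dengue, −10% for T and D.

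The cost is one sentence in each document, plus the optional edit. No new data are needed, and sample size, power and analysis methods stay as they are.

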##### *Tdap Immunogenicity:*

- Ab concentrations against PT, FHA, PRN, and FIM2+3, as measured by ELISA, at baseline (D0 for group 2, M1 for Group 1) and 28 days after the dose of Tdap vaccine
- Anti-T and anti-D Ab concentrations  $\geq 0.1$  IU/mL, as measured by ELISA for T and by MIT-TNA for D, at baseline (D0 for group 2, M1 for Group 1) and 28 days after the dose of Tdap vaccine

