3.1 Trial Design

This is a Phase IIIb, randomized, open label, multicenter study in 688 healthy subjects aged 9 to 60 years in the Philippines.

Subjects were to receive the CYD dengue vaccine according to a 3-dose schedule, given 6 months apart. A booster dose of Tdap vaccine (Adacel®) was to be administered either concomitantly to or before (sequential administration) the first dose of CYD dengue vaccine.

Subjects were to be randomized according to a 1:1 ratio into one of the 2 following groups with stratification on age (9 to 11 years, 12 to 17 years, 18 to 45 years and 46 to 60 years):

- **Group 1:** subjects were to be administered the first dose of CYD dengue vaccine concomitantly with the booster dose of Tdap vaccine at the second visit (V02; M1)
- **Group 2:** subjects were to receive Tdap vaccine at the first visit (V01; D0), and then CYD dengue vaccine 28 days later at the second visit (V02; M1)

The stratification was to be considered in order to balance the potential difference in terms of booster response by age group for the pertussis antigens (PT, FHA, PRN and FIM2+3).

Since the CYD dengue is to be administered according to a 3-dose schedule, given 6 months apart, initial trial design included administration of the second and third doses of CYD dengue vaccine at V04 (Month 7 [M7] and at V06 (M13) in all subjects.

At the time of study hold linked to the recommendation from IDMC not to vaccinate seronegative individuals anymore based on the results of the exploratory case-cohort study, all but 19 subjects (from both, Group 1 and Group 2) did receive dose 2 of the CYD dengue vaccine as planned. Following the IDMC recommendations, Sanofi Pasteur paused all vaccinations in CYD66 study, determined baseline serostatus and the Principal Investigators have communicated serostatus information to subjects already included in the study. In addition, the study protocol was amended to reflect the IDMC recommendations. The Sponsor has not received any feedback nor approval for the protocol amendment from Philippines FDA and has therefore decided to put an end to the CYD66 study with a last visit (which served as termination visit) of the subjects in order to inform them of the end of the study and to perform the last safety follow up. As a consequence, no more CYD dengue vaccine were administered to any subjects included in the study since the study hold. More details will be mentioned in the CSR

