4.4.2.5 Tdap Booster response

The booster response against pertussis components (PT, FHA, PRN and FIM2+3) will be calculated based on Ab concentration rises between pre (D0) and post-vaccination (28 days after the dose of Tdap vaccine). The booster response is defined as:

- A post-vaccination Ab concentration $\geq 4 \times$ LLOQ when pre-vaccination concentration is $<$ LLOQ
- A post-vaccination Ab concentration $\geq 4 \times$ pre-vaccination Ab concentration when pre-vaccination concentration is \geq LLOQ but $< 4 \times$ LLOQ
- A post-vaccination Ab concentration $\geq 2 \times$ pre-vaccination Ab concentration when pre-vaccination concentration is $\geq 4 \times$ LLOQ

For each pertussis components (PT, FHA, PRN and FIM2+3), the derived indicator will be "Yes" for that test if the computed value meets the booster response definition, otherwise indicator will be "No".

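### The pertussis co-primary ANOVA is valid but omits the pre-Tdap concentration already collected in both groups, so the four pertussis tests give up some precision

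*SAP*

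**What the plan says.** SAP 5.1.1.1 bases the four pertussis tests on log10 post-Tdap concentrations: "The age-stratified CI will be calculated using an analysis of variance (ANOVA) model (type II analysis"), and names the four age groups as the stratifying factor. Protocol 12.1.1.1 has the same model: "The age-stratified CI will be calculated using an ANOVA model (type II analysis"). Neither document adds a baseline concentration to this model or to a sensitivity version of it.

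The baseline is measured. Protocol 9.2.1.1 lists the four pertussis antigens "as measured by ELISA, at baseline (D0 for group 2, M1 for Group 1) and 28 days after the dose of Tdap vaccine", and Table 7.1 allots blood for them at V01 in Group 2 and V02 in Group 1. Samples at vaccination visits are drawn before injection (footnote to the procedures table in both documents). Group 1 receives no vaccine before V02.

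The pre-Tdap values are used for before/after description (SAP 5.1.2.2), concentration ratios (SAP 4.4.2.1) and booster response, which "will be calculated based on Ab concentration rises between pre (D0) and post-vaccination" (SAP 4.4.2.5).

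**The concern.** Tdap is given here as a booster, so a subject's antibody level before the dose may well help to predict the level 28 days later. The plan allows for this elsewhere: its booster-response rule changes with the pre-dose level, and randomization was stratified by age to balance differences in pertussis booster response. The pre-dose concentration of the same antigen is a more direct measure of starting level than age group. Because it is taken before any study vaccine in both groups, adjusting for it cannot remove a treatment effect.

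Overall success requires every Tdap antigen and every dengue serotype to pass. FIM2+3 has the lowest printed power of the ten co-primary tests, so precision there bears directly on the global conclusion. Any non-zero correlation within age group that is left out makes the intervals wider than the collected data allow, and leaves chance baseline imbalance in the estimated GMC ratio.

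**Working it through.** **Inputs from the documents.** SAP 5.5 gives "an alpha level of 2.5% (one-sided hypotheses), a maximum acceptable difference of 0.176 for GMCs". SAP 5.1.1.1 sets the margin: "non-inferiority limit is set at 1.5, i.e., 0.176". Allocation is equal: "Subjects were to be randomized according to a 1:1 ratio into one of the 2 following groups" (SAP 3.1). SDs on the log10 scale are PT and FHA 0.4, PRN 0.5 and FIM2+3 0.6; for dengue after dose 1 they are 1.0, 0.8, 0.8 and 0.7 with margin 0.301. The original evaluable size is 309 per group: "Considering a potential attrition rate of 10%, such sample size would provide 618 evaluable subjects" (SAP 5.5). The minimum for testing is 510, or 255 per group (SAP 5.7).

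**Assumptions not in the documents.** True difference 0 (this reproduces the printed tables); r, the correlation within age group between log10 pre- and post-Tdap concentration, taken as 0.3, 0.5 and 0.7 and equal for all four antigens; and the printed SDs read as residual SDs after age.

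**Formula.** Power = P(T > t₀.₉₇₅), where T is non-central t with 2n − 2 degrees of freedom and non-centrality margin / (SD × √(2/n)).

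**Reproducing the plan.** For FIM2+3 at n = 255 the standard error is 0.6 × √(2/255) = 0.0531 and the non-centrality is 0.176/0.0531 = 3.31, giving 91.1%. At n = 309 they are 0.0483 and 3.65, giving 95.4%. Both match the printed values. Multiplying the individual powers, with D and T taken as 1, gives 80.1% and 90.3%, against the stated 80% and 90%.

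**Adding the baseline.** The residual SD becomes SD × √(1 − r²). For FIM2+3 this is 0.572, 0.520 and 0.428 at r = 0.3, 0.5 and 0.7, with confidence intervals narrower by about 5%, 13% and 29%.

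| r (assumed) | FIM2+3, 255 | Global, 255 | FIM2+3, 309 | Global, 309 |
|---|---|---|---|---|
| 0 (as planned) | 91.1% | 80.1% | 95.4% | 90.3% |
| 0.3 | 93.4% | 82.9% | 96.8% | 92.1% |
| 0.5 | 96.8% | 86.9% | 98.8% | 94.2% |
| 0.7 | 99.6% | 89.8% | 99.9% | 95.4% |

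**Cap from the dengue tests.** These do not change. Their joint power is 0.9240 × 0.9887² × 0.9981 = 90.1% at 255 and 0.9621 × 0.9966² × 0.9996 = 95.5% at 309. Global power cannot exceed these values whatever r is.

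**Likely size.** SAP section 1 reports 629 seropositive subjects among the 676 given dose 1. With an equal split (assumed, since the SAP does not break this down by group) that is about 314 per group before other per-protocol exclusions. Losing a further 10% (assumed) would leave 629 × 0.9 / 2 = 283 per group. There, planned power is 93.6% for FIM2+3 and 86.2% globally, rising to 95.5% and 88.5% at r = 0.3.

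**If there is some true interference.** With Group 1 truly 0.05 log10 lower (assumed), FIM2+3 power at 255 per group goes from 65.8% to 69.9%, 78.0% or 91.2%; at 309 it goes from 74.1% to 78.0%, 85.3% or 95.4%.

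**The case against.** The strongest reply is that this is a preference about efficiency. Randomization was stratified by age, the model includes that stratum, the test keeps its alpha, and the printed power meets the plan's 90% target at 309 per group without a covariate. That stands. A reader might infer that the co-primary comparison is biased or invalid, but the documents do not support this: chance imbalance after randomization is already reflected in the interval, and baseline remains visible through the descriptive summaries, ratios and booster response.

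A reader might also take the baseline to be a strong predictor. No correlation is given. The booster-response rule defines what counts as a response; it does not show how closely pre- and post-dose concentrations track each other. If age already explains part of the 0.6 SD, the planned ANOVA has more power than the tables show. Nor is 80% global power the expected position: it belongs to the minimum size, and the 629 seropositive subjects point to something larger.

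There is also a fair point about timing and rules. The trial is open label, the SAP describes subject visits as finished, SAP 5.3.2 rules out imputing missing immunogenicity values, and the per-protocol set for Tdap (PPT) does not require a pre-Tdap result. Changing a co-primary model late needs a record that the choice was not driven by results. This shapes the fix. It does not remove the gain, because the covariate is already collected and costs about one degree of freedom if r is zero.

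**Conclusion.** The point holds as a worthwhile improvement to a valid analysis. Over the assumed range of r from 0.3 to 0.7, adjustment adds about 2 to 9 percentage points to FIM2+3 power at 255 per group and about 1 to 5 points at 309. It adds about 3 to 10 points and 2 to 5 points respectively to global power. Gains at the size probably reached lie between these. They apply to the pertussis tests only; dengue serotype 1, at 92.4% for 255 per group, is nearly as weak as FIM2+3 and is unaffected. The direction is secure for any appreciable r, but its size cannot be fixed from the documents.

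**What to change.** Before database lock, change SAP 5.1.1.1 so that, for each pertussis antigen, log10 post-Tdap concentration is modelled on group, age stratum and log10 pre-Tdap concentration of the same antigen (V01 in Group 2, V02 in Group 1; values below LLOQ set to half LLOQ, as SAP 4.4.2.1 already does for GMCs). Take the 95% CI of the group difference from this model and compare its lower bound with −log10(1.5). List the change in SAP 5.7 as a departure from protocol 12.1.1.1.

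For the few subjects without a pre-Tdap result, choose one rule in advance. Either fill the covariate (for example, overall mean plus a missing indicator), stated as an explicit exception, for the covariate only, to the no-imputation rule in SAP 5.3.2; or analyse subjects with both samples. Report the age-only ANOVA on all PPT subjects as the supporting analysis.

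Two small edits belong with this. SAP 4.4.2.5 labels the pre-dose value D0, which does not fit Group 1. SAP 5.1.1.2 describes a normal-approximation interval for GMCs without mentioning age, so the SAP should say which interval is primary.

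The cost is one model term, a missing-baseline rule and a documented departure from the protocol model; no new data are needed. If the database is already locked, the adjusted model should be presented only as a supporting analysis and labelled as added late.
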